## **9.2 Pharmacodynamics**

The analysis of the PD data will be performed on the PD-PPS. All listings will be presented for the SS.

### **9.2.1 Total Serum IgG**

Total Serum IgG concentrations and IgG subclasses will be listed by treatment group and timepoint including absolute changes from Baseline and percentage changes from Baseline. Descriptive summaries (including n, arithmetic mean, median, SD, minimum and maximum) will be presented by treatment group and timepoint for absolute values, changes from Baseline and percentage changes from Baseline.

Further descriptive summaries (including n, arithmetic mean, median, SD, minimum and maximum) will be presented by treatment group, timepoint and █ status (6 categories; see Section 9.3.2) for absolute values, changes from Baseline and percentage changes from Baseline.

Participant total Serum IgG will be plotted against planned time. Mean Serum IgG, mean change from Baseline and percentage change from Baseline will be plotted against planned time by treatment group.

For each participant, the minimum value and maximum decrease (absolute and percentage) from Baseline in total serum IgG concentration during the study (using all available data up to cut-off point) will be listed. The minimum value and maximum decrease will be summarized by treatment group. In the event that a decrease from Baseline in IgG is not observed in a given participant, the maximum decrease will be reported as the smallest increase from Baseline.

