## 2 INTRODUCTION

Chronic inflammatory demyelinating polyradiculoneuropathy is a rare disorder of the peripheral nerves characterized by chronic and progressive onset of weakness, loss of sensation, reflexes, reduction or partial block in motor nerve conduction, and often pain and imbalance. Worldwide, the prevalence of CIDP ranges from approximately 1 to 9 cases per 100,000 (Mathey et al, 2015). For many patients, CIDP results in substantial disability, limiting their activities resulting in an overall negative impact on quality of life across multiple dimensions. Progressive disease and/or relapses can result in difficulty moving arms, hands, legs, and feet, a loss in the ability to walk independently or confinement to wheelchairs and reliance on caregivers (Mahdi-Rogers et al, 2014). Healthcare costs for CIDP are substantial (Guptill et al, 2014; Mahdi-Rogers et al, 2014; Olesen et al, 2012).

Cellular and humoral immune mechanisms are thought to be involved in the pathogenesis of CIDP resulting in inflammatory lesions in the spinal roots, proximal nerve trunks and along the peripheral nerves. The essential role of the autoimmune antibodies in mediating this pathology is supported by the improvement seen after plasma exchange (PLEX) and immunoabsorption (IA). Identification of the specific antigenic target(s) of the autoimmune antibodies in CIDP is expanding with recent immunological techniques.

Although the prognosis of CIDP has markedly improved over the last decades, significant disability remains. High dose steroids, PLEX, IA, and IVIg and SC Ig have all been shown to be effective treatments for CIDP. However, comorbid diseases including hypertension, diabetes, and psychiatric diseases limit the use of high dose steroids. While PLEX is effective, the procedure is burdensome for patients. Immunoglobulin treatment (IVIg and SC Ig) is often used as first line treatment but there remains a medical need for improved therapeutic options.

The neonatal major histocompatibility complex (MHC)-class-I-like Fc receptor (FcRn) recycles IgG and albumin from most cells and transports it bi-directionally across epithelial barriers to affect systemic and mucosal immunity. It has been shown that FcRn rescues both IgG and albumin from intracellular lysosomal degradation by recycling it from the sorting endosome to the cell surface (Anderson et al, 2006). Immunoglobulin G has a half-life of approximately

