#### **3.2 Secondary objectives**

The secondary objectives of the study are:

- To evaluate the safety and tolerability of rozanolixizumab sc infusion in subjects with CIDP

- To assess the PD effect of rozanolixizumab as measured by the total IgG concentrations in serum

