### **5 STUDY DESIGN**

#### **5.1 Study description**

This is a Phase 2A, multicenter, randomized, subject-blind, investigator-blind, placebo-controlled, parallel-group study evaluating the efficacy, safety, and tolerability of rozanolixizumab for treatment of subjects with CIDP. Eligible subjects will be adults who have a confirmed diagnosis of definite or probable CIDP according to the EFNS/PNS criteria for CIDP, have been shown to be dependent on treatment with immunoglobulin and who have remained on a stable dosing regimen of immunoglobulin therapy for at least 4 months prior to Screening.

- Treatment Arm 1: [REDACTED]  
[REDACTED]
- Treatment Arm 2: [REDACTED]  
[REDACTED]

See Section 7.2 for details on treatments to be administered.

Subjects will be randomized in a ratio of 1:1 to the 2 treatment arms. The randomization will take place on the day of first treatment with IMP. The randomization will be stratified according to previous route of administration for Ig treatment (ie, SCIG and IVIg).

The dose level of [REDACTED] may be reduced to [REDACTED] (or equivalent placebo) for an individual subject based on their tolerability (see Section 7.2 for details). For example, if a subject experiences a severe headache which does not respond to headache treatment (see Section 12.1.10), a decision to decrease future doses to [REDACTED] may be made. The decision to decrease the dose will be made following a discussion between the investigator and the UCB study physician. In addition, the decision to decrease the dose for the remainder of the subjects may be made following a DMC recommendation.

The study consists of:

- Screening Period of between 2 and 5 weeks duration. The purpose of the Screening Period is to evaluate and confirm the subject's eligibility. All subjects must have an Ig dependency that has been confirmed within 18 months before Screening. All subjects must be on a long-term immunoglobulin maintenance therapy with a stable immunoglobulin infusion regimen at consistent intervals to be considered eligible. The Screening Period will be a minimum of 2 weeks and generally should not exceed 5 weeks. During the Screening Period, the subjects will receive their last dose of immunoglobulin therapy before the randomization (see details in Section 8.2).

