dose was well-tolerated, and a summary of the safety results is included in the IB. However, it should be noted that the exposure of rozanolixizumab was lower in subjects with ITP than subjects with MG when dosed with the same dose level.

The dose-exposure-response relationship, with total IgG as the primary endpoint, was determined using non-linear mixed effects modeling of the data from UP0018. The derived population PK-PD (structural PK-PD model based on that of Lowe [Lowe et al, 2010]) was then used to guide, through simulation, the selection of appropriate repeat dose regimens that would mimic decreases achieved by plasmapheresis paradigms and result in an IgG reduction of 70% or greater. The model-based simulations demonstrate that the chosen dose regimen of [REDACTED] sc administered weekly for a total of 12 doses are expected to produce maximum mean IgG reductions of >70% over the Treatment Period. Based on simulations, it is expected that these IgG reductions will be reached rapidly and maintained consistently with the selected dosing regimen.

This study will utilize the same liquid formulation at [REDACTED] as was used in the first in human study. In the first in human study, individual dose was achieved by diluting the formulation prior to administration. Based on the heaviest subject (81kg) at the highest sc dose [REDACTED], the maximum concentration given was [REDACTED]. This change in concentration is not predicted to have an impact on local tolerability, however to allow this to be fully assessed

the first two infusions in each subject will be given at a slower rate of approximately [REDACTED]. If no tolerability concerns are identified subsequent infusions may be given at rates up to [REDACTED].

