#### **14.4.3 PD analyses**

For all PD variables, descriptive statistics for the value, change from Baseline, and/or percentage change from Baseline will be tabulated by treatment group, actual dose received, and time point.

The PD variables will include serum IgG, IgG subclass, and neurofilament light chain concentrations.

Population PK analyses and PK/PD analyses may be conducted for the PD variables of interest. All such PK and PK/PD analyses will be described in a separate Data Analysis Plan (DAP) however results will not be reported in the CSR.

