#### 2.1.2 Secondary objectives

The secondary objectives of the study are:

- To evaluate the safety and tolerability of rozanolixizumab subcutaneous (sc) infusion in subjects with CIDP
- To assess the pharmacodynamic (PD) effect of rozanolixizumab as measured by the total immunoglobulin G (IgG) concentrations in serum

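### Total IgG, a secondary objective, gets no placebo-adjusted estimate, although its Day 1 Baseline contains maintenance Ig that washes out in both arms

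*SAP*

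**What the plan says.** **Objective.** Protocol 3.2 lists among the secondary objectives: "To assess the PD effect of rozanolixizumab as measured by the total IgG concentrations in serum". SAP 2.1.2 repeats it.

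**Planned analysis.** SAP 9.2.1 gives descriptive summaries that "will be presented by treatment group and timepoint for absolute values, changes from Baseline and percentage changes from Baseline", with mean plots by treatment group. For the per-participant extremes, "The minimum value and maximum decrease will be summarized by treatment group". Protocol 14.4.3 is also descriptive: results are "tabulated by treatment group, actual dose received, and time point". No contrast, model or interval for IgG appears in either document. Protocol 14.4.3 allows population PK/PD modelling, but only as an option, under a separate plan and outside the study report.

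**Baseline and Ig background.**
- SAP Table 3-1 sets the total IgG Baseline at Day 1, with Screening as the fallback.
- Protocol 6.2.2 excludes anyone averaging under 0.4 g IgG/kg/month over the previous 4 months.
- Protocol 5.1: "During the Screening Period, the subjects will receive their last dose of immunoglobulin therapy before the randomization".
- Protocol 8.2 places Day 1 one week before the next planned IVIg dose (at the latest on that date), or on a planned SCIg day ±2 days.
- Protocol 7.7.2 prohibits IVIg and SCIg in both arms during the Treatment Period.
- Protocol Section 2: "Immunoglobulin G has a half-life of approximately" 3 weeks in man.

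**The concern.** The objective asks what rozanolixizumab does to IgG. In this design, change from Baseline does not answer that within one arm. The Day 1 value contains Ig given shortly before the trial, and both arms then stop Ig, so IgG should fall on placebo as well. The active arm's fall is drug effect plus washout, and only a comparison with placebo separates the two.

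The SAP makes such comparisons for variables that rank lower. iRODS gets a placebo-adjusted estimate with a 90% CI (SAP 8.1.2). Adjusted INCAT, both grip-strength measures and RT-MRC, all listed as other efficacy variables, get the same repeated-measures model. IgG, a named secondary objective, gets none. The report would then contain no estimate of the effect the objective names and no statement of its precision, with about 15 participants per arm (SAP 2.4).

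**Working it through.** **Is there a plan figure to reproduce?** The documents state no placebo-adjusted IgG effect. The only related figure is in the dose rationale (Protocol 5.4.4), where simulations sought regimens that would "result in an IgG reduction of 70% or greater". That model was built on the healthy-subject study and is not given in enough detail to rerun. The 70% is used below only as a reference value.

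**Inputs**
- Half-life: 21 days (Protocol Section 2, about 3 weeks).
- Time from Day 1: 84 days at Day 85 (Visit 17), 77 at Day 78 (Visit 16), 28 at Day 29 (Visit 9).
- Infused share *s* of Day 1 IgG: not in the documents. Assumed 10% to 50%.
- Also assumed: constant endogenous IgG and a single first-order half-life.

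**Step 1. Infused Ig remaining without drug,** *f* = 0.5^(t/21)
- Day 85: 0.5^4 = 0.0625, so about 94% is lost.
- Day 78: 0.5^(77/21) = 0.079, so about 92% is lost.
- Day 29: 0.5^(28/21) = 0.397, so about 60% is lost.

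**Step 2. Placebo IgG as a fraction of Baseline,** P = (1 − s) + s·f. At Day 85 this is 1 − 0.9375s.

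**Step 3. Reduction versus placebo when the active arm falls 70% from Baseline,** r = 1 − 0.30/P

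| Share s | P, Day 85 | Placebo fall, Day 85 | r, Day 85 | r, Day 78 | r, Day 29 |
|---|---|---|---|---|---|
| 10% | 0.906 | 9.4% | 66.9% | 67.0% | 68.1% |
| 20% | 0.813 | 18.8% | 63.1% | 63.2% | 65.9% |
| 50% | 0.531 | 46.9% | 43.5% | 44.4% | 57.0% |

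**Step 4. The converse.** If the true reduction versus placebo is 70%, the within-arm fall at Day 85 is 1 − 0.30·P: 72.8%, 75.6% and 84.1% for shares of 10%, 20% and 50%. That overstates the effect by about 3 to 14 percentage points.

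**Step 5. Can the effect be read from the planned tables?** Take s = 30% and a true reduction of 70%.
- Placebo: P = 1 − 0.9375 × 0.30 = 0.719, a fall of 28.1%.
- Active: 0.30 × 0.719 = 0.216, a fall of 78.4%.
- Difference of the percentage changes: 78.4 − 28.1 = 50.3 points, not 70%.
- Ratio of on-treatment levels: 0.216/0.719 = 0.30, which is the 70% reduction.

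The ratio recovers the effect. The difference of percentage changes does not.

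**Step 6. Samples after rescue.** SAP Section 8 invalidates measurements made after rescue medication, but it lists efficacy measures only. SAP 4.2.3, on PD data, has no such rule, and SAP 4.3 maps PEOT assessments, explicitly including PD, to scheduled visits. SAP 4.2.1 recognises that rescue can precede the PEOT visit. An IgG sample raised by rescue Ig could therefore enter a by-visit comparison, and would bias it if rescue differs between arms.

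**The case against.** The strongest reply is that placebo is not ignored. It is a displayed treatment group (SAP 3.1). SAP 9.2.1 tabulates absolute values as well as changes, summarises each participant's minimum by arm, and plots means by arm. Washout will be plain to see, and an unadjusted difference in mean IgG with an interval can be worked out from n, mean and SD. This stands. A reader might infer that IgG is judged solely by within-arm change with placebo unused, and the text of SAP 9.2.1 does not support that. What remains is that nobody is asked to produce an estimate, and the obvious shortcut of subtracting mean percentage changes gives the wrong quantity (Step 5).

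A reader might also infer that the trial will credit the drug with washout by holding the active-arm fall against 70%. No analysis section makes that comparison. The figure belongs to dose selection and is neither an endpoint nor a success criterion.

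The sizes above are also assumption-driven. The infused share is unknown. The dose rationale concerns maximum mean reductions expected to be reached rapidly, so Day 85 shows washout near its on-treatment peak and earlier visits show less. On a 6-week IVIg cycle, Day 1 falls 5 to 6 weeks after the last infusion, which favours a smaller share. All this limits the magnitude, not the direction.

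Finally, this is a small pilot, the protocol prespecified descriptive PD reporting, and SAP Amendment 2 removed tests to prevent overinterpretation. But the SAP kept 90% CIs for efficacy, and a ratio with a CI and no p-value follows the same approach.

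**Conclusion.** The point holds in this form: total IgG is assessed only descriptively by arm, without a placebo-adjusted estimate or interval, in a design where change from Baseline mixes drug effect with washout of prior Ig. That rests on the documents alone.

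The size does not. Under a 21-day half-life and constant endogenous IgG, a 70% within-arm fall at Day 85 corresponds to about 67%, 63% and 44% versus placebo for assumed shares of 10%, 20% and 50%. At Day 29 the figures are about 68%, 66% and 57%. These are illustrations and should not be read as a prediction that the drug's true effect is below 70%.

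The primary iRODS analysis and its sample size are unaffected. The change is worth making because a named secondary objective otherwise has no estimate, and it can be made from data already collected.

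**What to change.** Keep the descriptive tables and plots, and add the following to SAP 9.2.1.

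- **Model.** Repeated-measures model of log total IgG at scheduled visits up to Visit 17, on the PD-PPS, with treatment, visit, treatment-by-visit, log Baseline IgG and route of prior Ig. The covariance fallback sequence in SAP 8.1.2 can be reused, since IgG is drawn at 13 post-Baseline visits (4, 6, 7, 8 to 16, and 17) in about 30 participants.
- **Report.** Rozanolixizumab/placebo geometric mean ratio with 90% CI at each visit and no p-value, with Week 12 (Visit 16) as the headline.
- **Post-Ig samples.** Exclude from the model IgG samples taken after the first rescue or standard-of-care Ig, including PEOT samples mapped to scheduled visits, in line with the SAP Section 8 rule for efficacy data. That rule keeps same-day assessments, so state explicitly how same-day IgG samples are treated. Note also that the estimate then refers to IgG without further Ig and relies on the model's missing-at-random assumption.

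Cost: one extra model and one table from existing data.

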### **7.7.3      Rescue medication**

If, at any time during the Treatment and Observation Period, the subject relapses according to the predefined criteria for relapse as specified in Section [4.1.2](#) using the subject's score on iRODS, INCAT, or maximum grip strength (assessed by site personnel), and supported by the medical judgement of the investigator, then rescue medication must be considered and the subject will be withdrawn from IMP (see Section [6.4](#)). The subject will return to the SOC Ig treatment (eg, IVIg of 2g/kg) as rescue medication at the time of relapse at the discretion of the investigator. The subject will have the opportunity to be stabilized over a period of 2 weeks to maximum 12 weeks starting from the relapse visit (ie, PEOT or later visit; see Section [8.3](#)). Once stabilized, the subject who completed the Treatment Period with no CIDP relapse, will be offered the possibility to enter in the OLE (CIDP04) and be treated with rozanolixizumab from that moment onward. The subject will complete the FV (V21) and enter the OLE on the same day. If a subject relapses during Treatment Period or does not wish to enter the OLE, the subject will continue their SOC treatment after stabilization. They will continue the stabilization visit schedule (every 1 to 3 weeks) until they have a follow-up of 12 weeks after last IMP dose.

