#### **3.5.8 Pharmacodynamic Per-Protocol Set**

The Pharmacodynamic Per-Protocol Set (PD-PPS) is a subset of the FAS, consisting of those participants who had no important protocol deviation affecting the serum concentrations of total IgG, IgG subclasses, or neurofilament light chain. Post-Baseline deviations will not necessarily lead to total exclusion of a participant from the PD-PPS but may lead to exclusion of specific data.

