#### **4.3 Handling of measurements obtained at the premature end of treatment visit**

Participants who withdraw from the study prematurely will be encouraged to return for the PEOT visit. The following rules will apply with regard to the inclusion of the results obtained at the PEOT in the descriptive summaries:

- Any measurements (including efficacy, safety, immunological and PD assessments) conducted at the PEOT should be included in the summaries for the respective scheduled visit, if the PEOT occurs at the time of the next scheduled visit (within the tolerance window specified in the protocol).
- If the PEOT does not correspond to the day of a scheduled visit, the efficacy, safety and other relevant assessments of the PEOT should be mapped to the nearest scheduled visit, relative to the Baseline visit date, following the last scheduled visit where assessments are available.
- If the date of the PEOT is equidistant between 2 scheduled visits at which no scheduled assessments were performed, the assessments from the PEOT will be mapped to the earliest of these visits.

Different domains from the same PEOT may be re-assigned to different study visits depending on the study schedule of assessments ie, measurements obtained at the PEOT can only be mapped to a scheduled visit at which the respective assessment was intended to be measured. Assessments from the PEOT that are mapped to scheduled visits will be flagged in the data listings.

Visits after the PEOT following the schedule of the 12-Weeks Observation period, will be mapped to the corresponding planned visit. Assessments on these visits will be flagged in the data listing.

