## 8 EFFICACY ANALYSES

All analyses of the efficacy variables will be performed on the FAS. Additional outputs may be repeated for the PPS or the MFAS where indicated. Listings will be based on the SS.

Treatment group assignment for efficacy analysis will be according to the actual treatment regimen.

All efficacy analyses are to be interpreted as exploratory analyses. No p-values will be presented.

Any efficacy measurements are considered invalid, if the participant received rescue medication before the assessment. Assessments collected at the same day as first intake of rescue medication are considered valid. Respective measurements will not be used for summary tables and MMRM, but kept in listings. This includes iRODS, INCAT, clinician reported grip strength, RT-MRC, CIDP PRO and Fatigue, PGIS, PGIC and the patient reported grip strength as derived in Section 8.2.4.

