## 10.2 Adverse events

Adverse events will be recorded from the time of informed consent until study completion. All AEs will be coded (Section 3.8) and categorized by relationship to rozanolixizumab.

In addition, AEs will be classified according to the Common Terminology Criteria for Adverse Events (CTCAE) Version 5.0 for severity. For any AEs where it is not possible to provide a CTCAE grading, the events will be assessed using a standard intensity classification (mild, moderate and severe).

A TEAE is defined as any event that was not present prior the first administration of IMP or any unresolved event already present before the first administration of IMP that worsens in intensity following exposure to treatment until 8 weeks following the last administration of IMP. Adverse events starting before the first administration of IMP or later than 8 weeks after the administration of the last IMP will not be considered TEAEs. Such events will be listed only.

Where dates are missing or partially missing, AEs will be assumed to be treatment-emergent unless evidence exists that does not allow the AE to be treatment-emergent. Handling of missing dates/times for classification of AEs as TEAEs is described in Section 4.2.7.

The following rules will be used to assign a TEAE to the study periods:

1. **Treatment Period:** a TEAE will be assigned to the Treatment Period for the tabulations if the start date/time of the event is at the time of or after the first administration of IMP on Day 1, up to Visit 17/PEOT (non-inclusively).
2. **Observation Period:** a TEAE will be assigned to the Observation Period for the tabulations if the start date/time of the event is at or after Visit 17/PEOT till 8 weeks after administration of the last IMP.
  - The Observation Period's TEAEs will be stratified by TEAEs of participants who received/did not receive standard of care treatment (i.e. Ig treatment) between start of the Observation Period and occurrence of the TEAE.

The number and percentage of participants who experience TEAEs will be summarized by Treatment Period, Observation Period (standard of care treatment status identified by WHODD J06BA01 and J06BA02) and Overall with respective treatment group. The following summaries will be presented:

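### Total IgG and IgG subclass summaries have no rule for values sampled after rescue or standard-of-care immunoglobulin, which affects Visit 21 and any PEOT sample taken after Ig

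*SAP*

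**What the plan says.** The secondary PD objective in SAP 2.1.2 is: "To assess the pharmacodynamic (PD) effect of rozanolixizumab as measured by the total immunoglobulin G (IgG) concentrations in serum". SAP 9.2.1 serves it descriptively. Summaries of IgG and subclasses "will be presented by treatment group and timepoint for absolute values, changes from Baseline and percentage changes from Baseline". For each participant, the minimum value and maximum decrease "from Baseline in total serum IgG concentration during the study (using all available data up to cut-off point) will be listed". Neither statement mentions intervening immunoglobulin.

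Rescue is immunoglobulin. Protocol 7.7.3 states: "The subject will return to the SOC Ig treatment (eg, IVIg of 2g/kg) as rescue medication at the time of relapse". Protocol 5.1 also lets completers without relapse go back to SOC Ig for the Observation Period, and lets relapsed or withdrawn participants do so.

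Four other SAP provisions bear on the point:
- **SAP 8** makes efficacy measurements after rescue invalid for summaries and MMRM. On its scope it says: "This includes iRODS, INCAT, clinician reported grip strength, RT-MRC, CIDP PRO and Fatigue, PGIS, PGIC", followed by patient-reported grip strength. IgG is not in the list.
- **SAP 10.2** separates by Ig use: "The Observation Period's TEAEs will be stratified by TEAEs of participants who received/did not receive standard of care treatment".
- **SAP 4.3** does the reverse for PD: "Any measurements (including efficacy, safety, immunological and PD assessments) conducted at the PEOT should be included in the summaries" for the matching scheduled visit, or otherwise is mapped to the nearest one.
- **SAP 3.5.8** limits the PD analysis set to FAS participants with "no important protocol deviation affecting the serum concentrations of total IgG, IgG subclasses, or neurofilament light chain". It adds that post-Baseline deviations may lead to removal of particular data.

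**The concern.** Infused immunoglobulin raises serum IgG directly, so a sample taken after it measures drug effect and infusion together. The SAP recognises the problem for efficacy and for adverse events, where Ig acts less directly, but not for the variable that Ig changes most immediately.

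The sponsor also foresaw the sequence of events. SAP 4.2.1 covers a participant who gets rescue before the PEOT visit and declares that assessment invalid, but only for efficacy. SAP 14.2 places this change in Amendment 2, which followed a blinded data evaluation meeting.

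At stake is the reading of the IgG means at the affected visits. A mean that includes post-Ig values describes neither the effect of FcRn blockade nor the recovery after it stops.

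**Working it through.** There is no stated figure to reproduce: the IgG analysis is descriptive and the trial is not powered on it. The check is which IgG samples can follow Ig, and what the SAP does with them.

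**Step 1. Where post-Ig samples can arise** (Protocol Table 5-1, 6.4, 8.2 and 8.3)

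| IgG sample | Can it follow rescue or SOC Ig? | Handling in the SAP |
|---|---|---|
| Dosing Visits 4, 6, 8 to 16, and Visit 7 | No: rescue or relapse requires IMP to stop, which ends weekly sampling | By-visit summary |
| Visit 17 in completers without rescue | No: return to SOC is offered once this visit is done | By-visit summary |
| PEOT | Yes, if Ig was given before the sample | Mapped to a scheduled visit (4.3) |
| Visits 18 to 20 and stabilization visits | No IgG sample listed | None |
| Visit 21 / Final Visit | Yes, for anyone rescued or back on SOC Ig | By-visit summary |

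Exposure is therefore limited to two places. IgG is scheduled at every dosing visit, so a post-Ig PEOT value can land in a Treatment Period mean.

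**Step 2. Minimum value and maximum decrease.** Infused IgG pushes later values up. It cannot create a false minimum or a false maximum decrease, so these are largely protected although the window is the whole study.

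**Step 3. Size at an affected visit.** Inputs:
- n = 15 values: the per-group number in SAP 2.4, used here as an assumption for one visit.
- True fall 70%: Protocol 5.4.4 expects maximum mean reductions above this.
- Baseline 15 g/L and a rise of 10 g/L per affected value: assumptions, not in the documents.

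Uncontaminated mean = 15 × (1 − 0.70) = 4.5 g/L. With k affected values, mean = 4.5 + k × 10/15.
- k = 1: 4.5 + 0.67 = 5.17 g/L; fall = 1 − 5.17/15 = 65.6%.
- k = 3: 4.5 + 2.00 = 6.50 g/L; fall = 1 − 6.50/15 = 56.7%.

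To show the range, let each affected value instead have a percent change from baseline of between 0% and +50%:
- k = 1: (14 × −70 + 0)/15 = −65.3%, to (14 × −70 + 50)/15 = −62.0%.
- k = 3: (12 × −70 + 0)/15 = −56.0%, to (12 × −70 + 150)/15 = −46.0%.

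**Step 4. Direction.** The shift in an arm's mean is (k/n) × rise, upward in both arms. In the rozanolixizumab arm it hides part of the fall. In the placebo arm it raises the comparator. With three affected placebo values and one affected rozanolixizumab value, each of 15, the difference between arms widens by (3 − 1)/15 × 10 = 1.33 g/L. With the counts reversed it narrows by the same amount.

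**The case against.** **The PEOT normally comes first.** Protocol 8.4 puts PEOT as near as possible to the decision to withdraw, and 8.2 starts stabilization from PEOT. A post-rescue PEOT sample is then the exception, and because SAP 4.3 maps each PEOT to its own nearest visit, affected values would tend to scatter over the weeks. This stands as a limit on size: one affected value at a visit is a more natural case than three. It does not remove the gap, since SAP 4.2.1 provides for exactly this sequence.

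**The PD-PPS may already handle it.** Protocol 7.7.2 prohibits IVIg and SCIg in the Treatment Period, and the PD-PPS allows removal of specific data. The protocol deviation specification is a separate document, so it cannot be ruled out that some Treatment Period Ig counts as a deviation. But 7.7.2 refers to the rescue section, which provides for Ig at relapse, and return to SOC in the Observation Period is expressly allowed. Neither is evidently a deviation. Visit 21 is not covered, and the immunological analyses in SAP 9.3 use the Safety Set, without this filter.

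**The analysis is descriptive.** No test or decision rule in this SAP depends on it, and individual IgG plots and listings let a reader find affected values. This limits the importance of the point. The by-visit means and mean plots are still what a reader will look at first.

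**Who attends Visit 21 is unknown.** A reader might infer from Protocol Table 8-1 that nearly all attendees are on Ig. Completers entering the extension directly do leave at Visit 17, and participants testing whether they still need treatment are the clear Ig-free route. But the protocol says that relapsed or withdrawn participants can return to SOC, not that all do, and it gives no counts.

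**Conclusion.** The gap is real and narrow. The SAP has no rule for IgG and subclass values sampled after rescue or SOC Ig, and SAP 4.3 carries such PEOT values into visit summaries. Followed as written, the plan can mix infused IgG into the Visit 21 means and into any mean that receives a post-Ig PEOT value.

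Two stronger readings are tempting and not supported. The first is that the secondary PD objective as a whole is measured on infused IgG. The sampling schedule contradicts that: the other on-treatment visits are clean, and the minimum value and maximum decrease are largely unaffected. The second is that the drug effect is always understated. That holds within the rozanolixizumab arm, but the between-arm difference can move either way, depending on which arm has more affected values.

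The size rests on assumptions. With 15 values, a 15 g/L baseline, a true 70% fall and a 10 g/L rise, one affected value shows about a 66% fall and three about 57%. At Visit 21, about 12 weeks after the last dose, the 70% starting point need not apply, but the shift per affected value follows the same formula and grows as n falls. The wording should be corrected, but no test or sample-size figure changes.

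**What to change.** 1. In SAP 9.2.1 and 4.3, state that IgG and subclass values at PEOT-mapped visits, dated after the first rescue or SOC Ig administration, are listed but left out of by-visit summaries and mean plots. Treat same-day values as valid, as SAP 8 does for efficacy. A finer pre-infusion rule is not workable, because SAP 4.2.7 notes that times are not recorded for concomitant medication.
2. At Visit 21, do not exclude. Summarize IgG and subclasses, and the vaccine-antibody titres that the protocol also samples there, separately by Ig received since the last IMP dose (yes/no). Identify Ig with the medication codes already used in SAP 10.2.
3. State that values left out under item 1 do not count as missing for the 33% rule in SAP 4.2.3. Otherwise the exclusions could suppress the summaries they are meant to clean.

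The cost is SAP wording and a date-based flag from data already collected. The drawback is smaller n at PEOT-mapped visits and in the Visit 21 strata. Under SAP 3.1, a stratum with fewer than 3 values shows only n, minimum and maximum.
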